9.8 Imputation of Missing Data

Unless otherwise specified all data will be evaluated as observed, and no imputation method for missing values will be used, with the exception of:

- Handling of missing data for PK parameter calculations is discussed under Section 16.1;
- Handling of the following data, for which imputed values will be presented in all participant data listings and imputed information will be flagged:

| | |
|----------------|--|
| Adverse events | 
Incomplete AE-related dates will be imputed as follows:
 
• If the AE onset date is missing completely, then the onset date will be replaced by the start of study treatment. If the end date or resolution date indicates that the AE has stopped before start of treatment, this date will be used for imputation instead of start of treatment date.• If only the day part of the AE onset date is missing, but the month and year are equal to the start of study treatment, then the AE onset date will be replaced by the start of study treatment. For example, if the AE onset date is --/JAN/2015, and study treatment start date is 15/JAN/2015, then the imputed AE onset date will be 15/JAN/2015. If the end date or resolution date indicates that the AE has stopped before start of treatment, this date will be used for imputation instead of start of treatment date.• If both the day and month of the AE onset date are missing but the onset year is equal to the start of study treatment, then the onset date will be replaced by the start of study treatment. For example, if AE onset date is --/---/2014, and study treatment start date is 19/NOV/2014, then the imputed AE onset date will be 19/NOV/2014. If the end date or resolution date indicates that the AE has stopped before start of |
|----------------|--|

| | |
|------------------------------------|--|
| | 
treatment, this date will be used for imputation instead of start of treatment date.
 
 • In all other cases the missing onset day and/or missing onset month will be replaced by 1. • Incomplete stop date will be replaced by the last day of the month (if day is missing only), if not resulting in a date later than the date of participant's death. In the latter case the date of death will be used to impute the incomplete stop date. • In all other cases the incomplete stop date will not be imputed. If stop date of AE is after date of cut-off this date will be kept. 
Incomplete AE-related times will be imputed as follows:
 
 • If the AE onset time is missing, but the date is equal to the start of study treatment, then the AE onset time will be replaced by the start time of study treatment. • In all the other cases missing start time will not be imputed. • Incomplete stop times will not be imputed. |
| 
Concomitant Medications
 | 
For identification of previous or concomitant medications/procedures, no formal imputation will be performed on missing or incomplete dates. Rules presented in Table 2 will be used to define if a medication/procedure is considered as a previous, concomitant or both previous and concomitant medication/procedure.
 |
| 
Exposure
 | 
Incomplete exposure times will be imputed as follows:
 
 • If the first dose time is missing, then: 
 ○ if the first dose date is equal to date of randomization then the first dose time will be imputed as the time of randomization. ○ if the first dose date is after the date of randomization then the first dose time will be imputed: 
 ▪ as 08:00 if timing = “Morning” or unknown ▪ as 20:00 if timing = “Evening” • If the last dose time is missing, then, it will be imputed: 
 ○ as 08:00 if timing = “Morning” or unknown ○ as 20:00 if timing = “Evening”. |
| 
ICU admission and discharge
 | 
Incomplete ICU admission dates will be imputed as follows:
 
 • If the ICU admission day is missing, it will be imputed as the latest between 1st day of the month and the date of hospital admission. • In all other cases ICU admission date will not be imputed |

| | |
|--------------------|---|
| | 
Incomplete ICU times will be imputed as follows:
 
• If the ICU admission time is missing, but the date is equal to the start of study treatment, then the ICU admission time will be replaced by the start time of study treatment.• In all the other cases, ICU admission time will be imputed as 00:00.• Incomplete discharge times will be imputed as 23:59, if not resulting in a date and time later than the date and time of participant's death. In the latter case the time of death will be used to impute the incomplete discharge time. |
| Hospital discharge | 
Incomplete hospital discharge dates will be imputed as follows:
 
• If the hospital discharge day is missing, it will be imputed as the last day of the month.• In all other cases hospital discharge date will not be imputed |

Table 1 Stopping rules for medication/procedure end dates

| End date of medication/procedure | | | Rules to derive medication/procedure stop |
|------------------------------------|-------------------------------------|---------------------------|---|
| Day | Month | Year | |
| UNK | UNK | UNK | After treatment start (ongoing) |
| UNK | UNK | < Treatment start (year) | Before treatment start |
| UNK | UNK | >= Treatment start (year) | After treatment start |
| UNK | < Treatment start (month and year) | | Before treatment start |
| UNK | >= Treatment start (month and year) | | After treatment start |
| < Treatment start (complete date) | | | Before treatment start |
| >= Treatment start (complete date) | | | After treatment start |

UNK = Unknown

Table 2 Rules to define previous and/or concomitant medication

| Start date of medication/procedure | | | Stopping rule (see Table 1) | Medication/procedure |
|------------------------------------|-------------------------------------|---------------------------|-----------------------------|--------------------------|
| Day | Month | Year | | |
| UNK | UNK | UNK | Before treatment start | Previous |
| UNK | UNK | UNK | After treatment start | Previous and concomitant |
| UNK | UNK | <= Treatment start (year) | Before treatment start | Previous |
| UNK | UNK | <= Treatment start (year) | After treatment start | Previous and concomitant |
| UNK | UNK | > Treatment start (year) | After treatment start | Concomitant |
| UNK | <= Treatment start (month and year) | | Before treatment start | Previous |
| UNK | <= Treatment start (month and year) | | After treatment start | Previous and concomitant |
| UNK | > Treatment start (month and year) | | After treatment start | Concomitant |
| <= Treatment start (date) | | | Before treatment start | Previous |
| <= Treatment start (date) | | | After treatment start | Previous and concomitant |
| > Treatment start (date) | | | After treatment start | Concomitant |

UNK = Unknown

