14.2.5 Time to ICU Admission (Day 1 Through Day 28)

Time to ICU admission will be based on data collected on the ‘Hospitalization’ eCRF page.

Time to ICU admission is defined as the time from first dose (Day 1) to the date/time of ICU admission, or death, whichever occurs first, in days:

- Time to ICU admission (days) = (Date/time of ICU admission – Date/time of first dose)

The rules below to define censoring/event dates will be followed:

| # | Description | Date of Event or Censoring | Outcome |
|---|---|----------------------------------|----------|
| 1 | Subject with first dose administered while in ICU | Date of first dose of study drug | Censored |

| | | | |
|---|---|---|----------|
| 2 | ICU admission or Death from Day 1 up to D28 | Earliest between date of ICU admission and date of death (in case of death) | Event |
| 3 | For subjects never admitted to ICU and not died | Earliest between D28 and date of discontinuation | Censored |

Number and percentage of subjects with and without the event will be summarized.

The hypotheses that will be tested for each dose level using a one-sided stratified log-rank test of time to ICU admission with use of corticosteroids at a prednisone equivalent daily dosage of ≤ 15 mg or > 15 mg within 48 hours prior to randomization, and country as stratification factors, are:

- H_{0i} : $HR_i \geq 1$
- H_{1i} : $HR_i < 1$

where

- HR_i denotes the Hazard Ratio of M5049 dose i versus placebo
- i denotes M5049 50 mg BID or M5049 100 mg BID
- $HR_i < 1$ denotes an improvement compared to placebo.

Estimation of effect each treatment dose (and 95% two-sided CI) separately compared to placebo will be based on hazard ratio from stratified Cox-model of event hazard rate, with terms for treatment arm (each active treatment separately against placebo), use of corticosteroids at a prednisone equivalent daily dosage of ≤ 15 mg or > 15 mg within 48 hours prior to randomization, and country. Ties will be handled using the discrete method.

Event-free survival function for time to event will be estimated via Kaplan-Meier (product-limit) method by treatment group and presented in a tabular and graphical format together with associated statistics (median time to event, event rates at Day 7, Day 14, Day 21 and Day 28) including the corresponding two-sided 95% CI. The estimates of the standard error (SE) will be computed using Greenwood's formula.

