14.2.8 Total Days in ICU

Total days in ICU will be based on data collected on the ‘Hospitalization’ eCRF page.

Total days in the ICU are defined as the sum, for all ICU admissions, of the time from ICU admission to the date of ICU discharge, in days:

$$\text{Total days in the ICU (days)} = \sum_h (\text{Date/Time of ICU discharge} - \text{Date/Time of ICU admission})$$

where h = number of ICU admissions during the study.

In case of ICU admission and discharge prior to first dose, the occurrence will not be considered for derivation of total days in ICU. In case ICU admission prior to and discharge after first dose, date and time of first dose will be used in place of date and time of ICU admission for calculation of total days in ICU.

The following information will be presented:

- Number and percentage of participants admitted in ICU
- Number and percentage of participants with more than one ICU admission
- Number and percentage of participants in the following discharge categories: death in ICU, discontinuation in ICU, discharged from ICU.
- Summary statistics of duration of ICU stay.

Participants never admitted to ICU will not be considered for descriptive statistics derivation.

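### A missing ICU admission day can be imputed to before first dose, and SAP 14.2.5 read literally then censors an on-treatment ICU admission at time zero

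*SAP*

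**What the plan says.** **Date rule.** When only the day of ICU admission is missing, SAP 9.8 states that "it will be imputed as the latest between 1st day of the month and the date of hospital admission". First dose plays no part in this rule.

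**Time rule.** The clock-time rule in the same table does refer to first dose: "If the ICU admission time is missing, but the date is equal to the start of study treatment", the time becomes that of first dose. Otherwise, "In all the other cases, ICU admission time will be imputed as 00:00".

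**Endpoint.** SAP 14.2.5: "Time to ICU admission is defined as the time from first dose (Day 1) to the date/time of ICU admission, or death, whichever occurs first". Row 1 of its event table, "Subject with first dose administered while in ICU", is censored at first dose. Row 2, "ICU admission or Death from Day 1 up to D28", is the event. Row 3 censors participants who neither entered ICU nor died.

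**Adverse events.** In the same SAP 9.8 table, if only the onset day is missing and the month and year match treatment start, "then the AE onset date will be replaced by the start of study treatment". An end date before treatment overrides this.

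**The concern.** Participants are in hospital, or being admitted, when they are screened (Protocol 5.1, criterion 7), and screening can take up to 48 hours. Hospital admission therefore normally falls on or before first dose, and SAP 14.2.9 provides for the case where it falls before. A rule tied to the hospital admission date can thus place an ICU admission ahead of dosing when it really happened on treatment. The participant then looks as if first dose was given in ICU. A deterioration event would be replaced by a censored observation with no follow-up. With about 50 participants per arm (150 randomised 1:1:1), a single lost event is visible in the result.

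**Working it through.** The plan gives no figure to reproduce here, so the check applies the rule to dates.

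**Formula.** Let F be the 1st of the ICU month, H the hospital admission date, D the first dose date and T the true ICU admission date, with T after D. The imputed date is I = max(F, H). It falls before D only if both F < D and H < D. Because T is after D, F < D means that the ICU admission is in the same calendar month as first dose and that first dose was not on the 1st. H < D means a lag of at least one day from hospital admission to dosing.

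**Worked dates**

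| H | D | T | I | I − D (days) | Reading under 14.2.5 | True time (days) |
|---|---|---|---|---|---|---|
| 5 Mar | 7 Mar | 15 Mar | 5 Mar | −2 | Row 1: censored at 0 | 8 |
| 30 Jan | 2 Feb | 8 Feb | 1 Feb | −1 | Row 1: censored at 0 | 6 |
| 12 Jan | 12 Jan | 18 Jan | 12 Jan | 0 | Not stated | 6 |
| 25 Jan | 27 Jan | 3 Feb | 1 Feb | +5 | Row 2: event, dated early | 7 |

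**Why row 1 follows in the first two cases.** The imputed stay starts before first dose and ends after it, which is what row 1 describes. The ICU date lies outside row 2's window, which opens on Day 1. Row 3 does not fit either, because the participant did enter ICU. If row 1 were set aside, the 14.2.5 formula would give a negative time (5 − 7 = −2 days in the first case). No passage exempts imputed dates.

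**The third case.** With same-day admission and dosing, a missing time is set to the first-dose time. The SAP does not say whether that is an event at time zero (row 2) or a censoring (row 1).

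**Share of records affected.** The lag from hospital admission to dosing is not in the documents. As an illustration, assume hospital admission is equally likely on each of 365 dates and the true ICU day is evenly spread over a window after first dose. For on-treatment ICU admissions with a missing day:

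| Lag, H to D | Imputed date | T 1–7 days after D | 1–14 days | 1–27 days |
|---|---|---|---|---|
| 1, 2, 3, 5 or 7 days | before D | 84% | 72% | 51% |
| | on D | 3% | 3% | 3% |
| | after D | 13% | 25% | 46% |
| 0 days | before D | 0% | 0% | 0% |
| | on D | 87% | 75% | 54% |
| | after D | 13% | 25% | 46% |

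The five non-zero lags agree because the condition asks only whether H precedes D.

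**Weight of one record.** If an arm had 5 to 10 ICU or death events (an assumption), one lost event is 1/10 to 1/5, or 10% to 20%, of them.

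**With a floor at first dose.** In the first case, max(1 March, 5 March, 7 March) = 7 March. Provided row 1 is limited to documented stays, this is a row 2 event at day 0 instead of day 8.

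**The case against.** The trigger is narrow. It needs a known month but an unknown day for a transfer within hospital, where clinical status is scored daily. Source data are monitored, a data review meeting precedes lock, and imputed values are flagged in listings. The SAP treats all tests as exploratory. Row 1 also describes a fact, and the SAP nowhere says that an imputed date establishes it. Eligible participants are randomised at once (Protocol 9.1.1), so same-day admission and dosing is possible, and then no date falls before first dose. All of this stands and lowers the importance. It does not supply the missing floor or say which row applies.

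Four stronger readings are tempting, and the documents do not support them.

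- **That the imputed date is usually before first dose.** This depends on a lag that is not given: 0% at lag zero, and 51% to 84% at a day or more under assumed ICU timing.
- **That a later death is also lost.** Row 2 covers death up to Day 28, and no order between rows 1 and 2 is stated.
- **That the missing floor lengthens total ICU days.** SAP 14.2.8 already says: "In case ICU admission prior to and discharge after first dose, date and time of first dose will be used in place". A floor gives the same start, so any overstatement comes from the unknown day itself.
- **That the adverse event rule always anchors to treatment start.** When only the day is missing, it does so only if month and year match treatment start. Otherwise the day becomes the 1st. The matching month is, however, exactly the situation in which the ICU rule fails.

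Nor do the documents give any reason to expect incomplete ICU dates to differ by arm in this double-blind trial.

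**Conclusion.** The point holds as a gap between SAP 9.8 and 14.2.5, and it is minor. When hospital admission precedes first dose by at least a day and the 1st of the ICU month also precedes it, an on-treatment ICU admission with a missing day is dated before dosing. On a literal reading it is then censored at time zero. When the ICU month is later than the first-dose month, the event is kept but can be dated early. With same-day admission and dosing, the outcome is undefined.

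Two things are assumed: that row 1 is judged on the imputed date (14.2.5 uses the Hospitalization eCRF page and describes no separate indicator of being in ICU at first dose), and that at least one such record exists. The likely effect is nil or a lost event or two on a secondary, exploratory endpoint.

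**What to change.** In SAP 9.8, when the ICU admission day is missing, impute the latest of the 1st of the month, the hospital admission date and the first dose date/time, but not later than ICU discharge or death. Make an exception where another record shows that the ICU stay began before first dose.

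In SAP 14.2.5, apply row 1 only when an ICU stay at first dose is documented by a non-imputed date, so that an imputed admission at first dose counts under row 2. Both edits are needed, because a floored date alone could still be read under row 1.

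The cost is two sentences and a small programming change. The downside is timing: the event is kept but may be several days early (day 0 instead of day 8 in the example). A stay that really began before dosing, with no record to show it, would count as an event. Total ICU days in 14.2.8 do not change.

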Serum virology (hepatitis B and C screening, HIV)	X														Data collected from chart: virology status is to be documented per local guidelines. A positive test result is NOT exclusionary but for participant management. Evaluations to be performed by local laboratory.	
Urine for drugs of abuse	X													X	Data collected from chart: status to be documented per local guidelines. A positive test result for nonprescribed drugs is NOT exclusionary but for participant management. Evaluations to be performed by local laboratory.	

Assessments and Procedures	SCR	Intervention Period (Days)							Continued Surveillance		Safety Follow-up		Relapse Admission ^a	Notes	
							HD/ET	EoT				EoS			
	(up to 48 hours before Day 1)													HD assessments should occur if participant discharged after Day 3 and before Day 14. ET (early termination of treatment) Visit should occur within + 24 hours of treatment discontinuation.	
Study Day		1	2	3	5	7	10		14	21	28	44	60	5 to 60	
Visit Window			± 6 h		± 12 h		± 24 h			+ 2 days		± 5 days	± 7 days	± 6 h	
Clinical Assessments and Study Intervention															
Study intervention administration		←Throughout 14 days→						X						X	Every 12 hours ± 2 hours for 14 days (4 tablets in the morning and 4 tablets in the evening).
Study intervention accountability		←-----Throughout (daily)-----→												X	Date and time of study intervention administration should be recorded daily, if discharged before EoT, date and time to be recorded on diary card.
Clinical surveillance scoring (9-point ordinal scale)		←-----Once daily during hospitalization (incl. predose on Day 1) and at the time of hospital discharge. After hospital discharge, then at study visits (e.g., Days 3, 5, 7, 10, 14, 21, 28, 44, and 60) and clinical status change-----→												Record each day throughout hospitalization at the first assessment of a given study day and at the time of hospital discharge; after participant is discharged, either via telemedicine contact or by return to study site at the times indicated only. The scale includes information such as hospitalization discharge, ICU stay, mechanical ventilation.	
Adverse event review		←-----Throughout-----→												Record each day at approximately the same time throughout hospitalization; if participant is discharged, either via telemedicine contact or by return to study site at the times indicated only.	

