9.6 Conversion Factors

The following conversion factors will be used to convert days into months or years:

1 week = 7 days, 1 month = 30.4375 days, 1 year = 365.25 days.

If height is recorded in inches, height (cm) = height (in) × 2.54.

If weight is recorded in pounds, weight (kg) = weight (lbs) ÷ 2.2046.

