14.2.9 Total Days in the Hospital and Time to Hospital Discharge

Total days in the hospital will be based on data collected on the ‘Hospitalization’ eCRF page.

Total days in the hospital are defined as the sum, for all hospitalization events, of the time from first dose to the date of hospital discharge, in days:

- Total days in the hospital (days) =
 First hospitalization: *Date of hospital discharge – Day 1 + 1*
 +
 Subsequent hospitalization: *Date of discharge – date of admission + 1*

In other words, in case of hospital admission prior to and discharge after first dose, date of first dose will be used in place of date of hospital admission for calculation of total days in the hospital. In case of multiple hospitalizations, the total number of days of each event will be added up.

The following information will be presented:

- Number and percentage of participants with more than one hospital admission (only non-consecutive hospitalization will be included in the count)
- Number and percentage of participants in the following discharge categories: death in hospital, discontinuation in hospital, discharged from hospital.
- Summary statistics of duration of hospital stay.

In addition, time to hospital discharge will be based on data collected on the ‘Hospitalization’ eCRF page from Day 1 through Day 28.

The time to hospital discharge, defined as the time from first dose (Day 1) to the date of first hospitalization discharge, in days:

- Time to hospital discharge (days) = (Date of first hospitalization discharge – Date of first dose)

The rules for the different types of censoring/event below will be followed:

| # | Description | Date of Event or Censoring | Outcome |
|---|-------------|----------------------------|---------|
|---|-------------|----------------------------|---------|

| | | | |
|---|---|--|----------|
| 1 | Death from Day 1 up to D60/Study completion | D28 | Censored |
| 2 | Failure at any point and time during the study from D1 up to D28, defined as: * ICU admission leading to treatment discontinuation * use of mechanical ventilation * relapse | D28 | Censored |
| 3 | Hospital discharge before Day 28 | Date of hospital discharge | Event |
| 4 | No hospital discharge before Day 28/discontinuation without death or failure | Earliest between D28 and date of discontinuation | Censored |

Analyses will be performed as specified in Section 14.2.3.

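### A missing hospital discharge day is imputed as month end with no upper bound, overstating each affected stay and sometimes censoring a true discharge before Day 28

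*SAP*

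**What the plan says.** SAP 9.8, for hospital discharge: "If the hospital discharge day is missing, it will be imputed as the last day of the month". The only other provision is "In all other cases hospital discharge date will not be imputed", so no bound is stated anywhere in the rule. The adverse-event stop-date rule in the same section also moves a missing day to month end, but only "if not resulting in a date later than the date of participant's death"; otherwise the date of death is used.

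The discharge date feeds two secondary endpoints in SAP 14.2.9, both taken from the Hospitalization eCRF page:

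- Total days in hospital is built from "the time from first dose to the date of hospital discharge" for the first stay, plus the length of any later stay.
- Time to hospital discharge is the first discharge date minus the first-dose date. A discharge before Day 28 is an event. Without one, and without death or failure, the participant is censored at the earlier of Day 28 and discontinuation.

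For the 9-point ordinal score, the schedule in Protocol 1.2 instructs sites: "Record each day throughout hospitalization at the first assessment of a given study day and at the time of hospital discharge". SAP 14.2.2 treats a score below 3 as discharged.

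**The concern.** Month end is the latest date compatible with the recorded month, so the error can only lengthen the stay. With no bound, the imputed date can contradict the trial's own records: it can fall after an outpatient visit, a readmission, death or last contact. In total days in hospital, a first stay stretched past a readmission overlaps the second stay, and the overlapping days are counted twice. In time to hospital discharge, a date pushed to Day 28 or later loses the event, and a smaller shift delays it. These records enter the stratified log-rank test, the Cox hazard ratio and the Kaplan-Meier discharge rates, because SAP 14.2.9 applies the analyses of SAP 14.2.3.

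The daily score, repeated at discharge, would usually give the missing day or bound it closely. The rule does not use it.

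**Working it through.** The plan gives no figure for this rule, so there is none to reproduce. The check is calendar arithmetic.

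**Inputs**
- Imputed date = last day of the recorded month (SAP 9.8).
- Day 1 = day of first dose, no Day 0 (SAP 9.4).
- Event only if discharge is before Day 28 (SAP 14.2.9).
- 150 participants randomised 1:1:1 (Protocol 4.1), so about 50 per arm.
- Assumption: discharge dates spread evenly over a 365-day year (seven months of 31 days, four of 30, one of 28).

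**Step 1: days added per affected record.** In a month of L days with true discharge on date d, days added are a = L − d, running from 0 to L − 1. The mean is (L − 1)/2: 13.5, 14.5 or 15.0 for L = 28, 30 or 31. The sum over a month is L(L − 1)/2, so over the year:

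(7 × 465 + 4 × 435 + 378)/365 = 5373/365 = 14.7 days, maximum 30.

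The SAP's own conversion, "1 month = 30.4375 days", gives the same: (30.4375 − 1)/2 = 14.7.

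**Step 2: event lost.** A true discharge on study day D is imputed to day D + a. It reaches Day 28 or later when a ≥ 28 − D, which holds for L − (28 − D) dates in a month of L days.

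| True discharge | Days added needed | Share imputed to Day 28 or later |
|---|---|---|
| Day 5 | 23 or more | (7×8 + 4×7 + 5)/365 = 89/365 = 24% |
| Day 10 | 18 or more | (7×13 + 4×12 + 10)/365 = 149/365 = 41% |
| Day 14 | 14 or more | (7×17 + 4×16 + 14)/365 = 197/365 = 54% |

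This cut-off follows the SAP's event row. Counting only dates strictly after Day 28 gives 77/365 = 21%, 137/365 = 38% and 185/365 = 51%.

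**Step 3: illustration.** Two participants are discharged on Day 10 with the day missing.
- First dose 20 January 2021: true discharge 29 January, imputed 31 January, Day 12. Event.
- First dose 25 January 2021: true discharge 3 February, imputed 28 February, Day 35. Censored.

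**Step 4: effect in an arm.** One affected record in an arm of 50 adds on average 14.7/50 = 0.29 day to the mean stay. It can remove one discharge event, 1/50 = 2 percentage points of a crude Day 28 proportion.

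**Step 5: where the missing death limit matters.** For time to discharge, SAP 14.2.9 censors every participant who dies up to Day 60 at Day 28, whatever the discharge date. For total days in hospital there is no such rule, so there the imputed stay can run past death.

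**The case against.** The strongest objection is that the rule will seldom be used. Discharge dates come from hospital charts, a score is required at discharge, discharge after Day 3 and before Day 14 triggers its own assessments (Protocol 4.4), and a data review meeting precedes database lock. If the day can be recovered from other records, a site query can recover it too. The endpoints are secondary in a study declared exploratory, imputed values are flagged in listings, and medians and quartiles are reported alongside means. All of this stands and limits the consequence. It does not justify a rule that, when used, can contradict the participant's own records.

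Several stronger readings are tempting but not supported:

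- A reader might infer that stays lengthen by 15 days on average in an arm. The 14.7 days applies only to records with a missing day, and no frequency is given.
- A reader might infer that the missing death limit distorts time to discharge. The censoring of deaths at Day 28 rules that out.
- A reader might cite the ICU rule, bounded "if not resulting in a date and time later than the date and time of participant's death", as a second comparator. That rule fills in a clock time, not a date; the adverse-event rule is the like-for-like comparison.
- A reader might infer that the error depends only on enrolment date. It is month end minus true discharge date, so it depends on enrolment date plus length of stay.
- A reader might infer that one arm is favoured. The rule is the same in every arm, and nothing suggests that missing days would differ between arms.

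The first outpatient score is not an exact substitute either. After discharge, scores are due only at visits or on a change of status, and visits are 7 days apart between Days 14, 21 and 28. It is an upper bound, not the discharge date.

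**Conclusion.** The concern holds per affected record. Under an even spread of discharge dates, the rule overstates the stay by about 14.7 days on average (maximum 30). It moves a true discharge on Day 5, 10 or 14 to Day 28 or later in about 24%, 41% or 54% of cases, turning an event into a censored record. Total days in hospital is overstated one for one and may run past death or overlap a readmission.

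The overall effect cannot be sized, because the documents do not say how often the day will be missing; it is probably seldom. Only total days in hospital and time to hospital discharge are touched. The primary endpoint, time to recovery, uses the date of the ordinal score and is unaffected. This is worth correcting because the rule as written gives wrong values and the correction is cheap, not because it threatens the trial's main conclusion.

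**What to change.** In SAP 9.8, replace the hospital discharge rule as follows:

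1. If the discharge day is missing, take it from the date of the ordinal score recorded at discharge.
2. If there is no such score, impute within the interval between the last inpatient record (score 3 to 7, since 8 is death) and the first outpatient record (score below 3), restricted to the recorded month. Name one convention in advance, for example the midpoint.
3. The result may never be later than the earliest of first outpatient contact, readmission, death and last contact.
4. Report the number of imputed discharge dates per arm beside both endpoints.

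Where the discharge-time score exists, no days are added and no event is lost. Even with no score at all, the midpoint between the later of first dose and the first of the month, and month end, would leave a mean error of about +4.5, +3.4 or +2.1 days for a true discharge on Day 7, 10 or 14, against +14.7 now.

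The cost is a few lines of SAP text and a small programming change before database lock. No new data are needed.
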